8. GENERAL ISSUES FOR STATISTICAL ANALYSIS

8.1 General Statistical Methodology

Descriptive summaries will be provided where appropriate for each of the primary and secondary variables.

Baseline characteristic and safety tables will be completed for the Safety Population unless otherwise specified. Baseline values are defined as the last non-missing measurement prior to the first dose of study drug. Change from baseline will be defined as the post-baseline visit value minus the baseline value.

Continuous, quantitative, variable summaries will include the number of patients (N) with non-missing values, mean and standard deviation, median, minimum, and maximum. Categorical, qualitative, variable summaries will include the frequency and percentage of patients who are in the particular category. In general the denominator for the percentage calculation will be based upon the total number of patients in the study population unless otherwise specified.

Efficacy tables will be presented for the ITT Population for each of the primary objectives. First, the number and proportion of subjects for each interval of NOAEL and LOAEL observed at the 48th month DBPCFC will be reported. This will be broken by baseline and other clinical characteristics. Non-parametric Kaplan-Meier estimates of NOAEL distribution with interval censoring will be used to report expected proportion of subjects within each interval of NOAEL and LOAEL, overall and by patient groups. Second, for each interval of NOAEL and LOAEL observed at the 48th month DBPCFC, Kaplan-Meier product limit estimates of the probabilities of loss of tolerance (as defined by the latter three efficacy outcomes in section 3.2.1 bullet 2) using interval censoring, will be plotted against time (17 weeks), overall and for various patient groups. The “expected” number of patients with loss of tolerance and the “P values” derived

from univariate log rank tests for interval censored data will be reported for each 48th month DBPCFC NOAEL.

Unless otherwise indicated, all statistical tests will be 2 sided and tested at a significance level of 0.05. Corresponding 95% confidence intervals will be presented for statistical tests.

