3.1.2 Secondary Objectives

The multifold secondary objectives include:

1. To evaluate the safety of SLIT regimen administered over initial 48 months of the study period.
2. To study the changes in immune parameters over time and compare these changes among subjects who were induced with clinical tolerance vs. those who failed.
3. To evaluate association of baseline characteristics with desensitization as assessed by the 48th month DBPCFC and with loss of desensitization as assessed by the final DBPCFC.

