3.2 Study Endpoints

3.2.1 Efficacy Endpoints

The primary efficacy endpoints are:

- An estimate of the dose as assessed by the 48th month DBPCFC, also called population sensitization threshold, predicted to provoke reactions in 5% and 10% of the peanut-allergic population. This will also give population level NOAEL and LOAEL that would define interval of consecutive administered dose levels within which the population sensitization threshold lies.
- Multiplicative or differential change in the population sensitization threshold as assessed by the 48th month DBPCFC with a unit change in covariates.
- An estimate of time to loss of desensitization for the following events:
 - Subject's true sensitivity threshold to reduce by half, also called half-life of sensitivity threshold.
 - Subject's true sensitivity threshold to maintain at the same level of LOAEL.
 - Subject's true sensitivity threshold to drop by at least one level of LOAEL.
 - Subject's true sensitivity threshold to remain at or above MCRT.
- Estimates of the proportion of patients at a fixed time for any of the above events that define loss of desensitization (bullet 2).
- Multiplicative change in hazard of loss of desensitization with a unit change in covariates.

Secondary efficacy endpoints include:

- Comparative estimates of changes in immune parameters over time among subjects who were induced with clinical desensitization versus those who failed.

- Incidence of all serious adverse events (SAEs) during the study.

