4.2 Double Blind Placebo Controlled Food Challenge (DBPCFC)

Protocol DBPCFCs will be administered on the subject at entry, 48 months and weekly during the seventeen-week tolerance phase by a nurse or physician who is blinded to the testing material. The supervising investigator will also be blinded to testing material. Before each challenge, the subject will have a physical exam and peak expiratory flow measurements performed.

The DBPCFC consists of two parts that will be randomly ordered. One part will consist of graded doses of peanut flour and the other of identical graded doses of placebo in the form of oat flour. The doses will be given every 10-20 minutes up to a cumulative dose of 1000 mg (25 mg, 50 mg, 100 mg, 250 mg, 575 mg) during the entry challenge and up to a cumulative dose of 5000 mg (100 mg, 200 mg, 500 mg, 800 mg, 1300 mg, 2100 mg) during the 48th month and final DBPCFC. There will be a minimum 10 minute observation period between doses to monitor for symptoms.

After administration of the first part of the challenge the subject will be observed for a minimum period of 1 hour prior to starting the second part. Reactions will be scored using a Food Challenge Symptom Score (FCSS) sheet. If the subject begins to have significant objective or persistent subjective symptoms, the food challenge will be terminated and the subject will be given appropriate treatment. Subjects who are symptomatic and receive treatment are observed for a minimum of 2 hours after the challenges are completed before being discharged from the clinical research unit.

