9.3 Demographics and Other Baseline Characteristics

Descriptive summaries of the demographic and other baseline characteristics will be completed for all enrolled patients in the study population, unless otherwise specified.

Descriptive summaries of demographic and other baseline conditions will include:

- Demographics
 - Age at onset of study (1-11 yrs)
 - Sex (M/F)
 - Age at introduction of peanut (0-11 yrs)
 - Daycare (Y/N)
- History
 - Concurrent eczema (Y/N)
 - Concurrent asthma (Y/N)
 - Concurrent allergic rhinitis (Y/N)
 - Parental history of atopic disease (Non/Mother/Father/Both)
 - C-section (Y/N)
 - Breastfeeding (Y/N)
 - Milk allergy (Y/N)
 - Egg allergy (Y/N)
- Clinical
 - Initial peanut skin test size (3mm-30mm)
 - Initial peanut IgE level (0.35-100kU/L)

Medical History will be coded using the latest version of MedDRA (version 16.0) and summarized by SOC and Preferred Term using frequency counts. Physical exam data will be presented in listings.

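### Covariate effects on loss of desensitization are tested separately within each month-48 NOAEL level (about 9 to 11 children each), for unnamed groups, at 0.05 with no multiplicity rule; one stratified analysis per named covariate would be better

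*SAP*

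**What the plan says.** **Tests.** For each NOAEL/LOAEL interval at the month-48 challenge, SAP 8.1 plans interval-censored estimates of the probability of loss, which "will be plotted against time (17 weeks), overall and for various patient groups". The groups are not named. The events are three, "as defined by the latter three efficacy outcomes in section 3.2.1 bullet 2": holding the LOAEL level, dropping at least one level, and staying at or above the MCRT. (They stand under the third bullet of 3.2.1, as SAP 8.1.1 has it.) P values derived "from univariate log rank tests for interval censored data will be reported for each 48th month DBPCFC NOAEL". Unless stated otherwise, "all statistical tests will be 2 sided and tested at a significance level of 0.05"; Protocol section 8 sets the same default.

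**Model.** SAP 10.1 fits a current-status model with an exponential loss rate for each dose interval, with and without covariates. It states no multiplicity rule either.

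**Candidate covariates.** SAP 9.3 lists 14 characteristics (4 demographic, 8 history, 2 clinical), introduced by "Descriptive summaries of demographic and other baseline conditions will include".

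**Role.** SAP 3.2.1 lists "Multiplicative change in hazard of loss of desensitization with a unit change in covariates" as a primary efficacy endpoint, as do the protocol synopsis and Protocol 2.2.1. SAP 3.1.2 lists as a secondary objective "To evaluate association of baseline characteristics with desensitization as assessed by the 48th month DBPCFC and with loss of desensitization", and Protocol 2.1 has the same aim as Objective #4, under its secondary objectives.

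**The concern.** Splitting the comparison by month-48 level cuts a small sample into very small strata and multiplies the number of tests. Each test can detect only an extreme difference, while the unadjusted 0.05 level lets chance findings accumulate. Because neither the groups nor any cut-points are named, the number of tests could be settled after the data are seen.

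Protocol Objective #4 hopes that predictors of response may in future help direct treatment to suitable patients. A covariate flagged in one stratum, on the outcomes of one or two children, is a weak basis for that. The conflict over role leaves open how much weight such a finding should carry.

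**Working it through.** **1. The plan's own figure.** The documents give no test count or error rate for these analyses. The only sample-size figure is 50, from the replaced two-arm design: 90% v 50% pass rates, 2:1 allocation, 80% power, two-sided 0.05. Without continuity correction this needs 15 + 30 = 45, and 45 / 0.9 = 50. The figure reproduces, but it concerns a different comparison.

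**2. Levels and stratum size.** SAP 4.2 lists the graded doses as "100 mg, 200 mg, 500 mg, 800 mg, 1300 mg, 2100 mg) during the 48th month and final DBPCFC".
- Read as single doses, four exceed 300 mg (500, 800, 1300, 2100).
- Read cumulatively, the levels are 100, 300, 800, 1600, 2900 and 5000 mg. Four exceed 300 mg; five are at or above it.
- Protocol Study Design, Protocol 5.5 and SAP 4 use more than 300 mg; the synopsis randomizes at 300 mg or more. These passages need reconciling, so both counts are carried.

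Protocol 5.2 expects about 45 children eligible for randomization: 45 / 4 is about 11 per level and 45 / 5 = 9, if evenly spread.

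**3. What one stratum can show.** Take 9 children split 4 v 5, with Fisher's test on lost/not lost as a simple stand-in for the log-rank test.
- Complete separation: p = 1/126 = 0.008.
- One child off: p = 6/126 = 0.048 (4 of 4 v 1 of 5) or 4/84 = 0.048 (3 of 4 v 0 of 5).
- Two children off: p = 0.17 to 0.21.

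Even with true loss probabilities of 80% v 20% (illustrative), power is about 0.8^9 + 0.8^4 × (5 × 0.2 × 0.8^4) + (4 × 0.8^3 × 0.2) × 0.8^5 = 0.134 + 0.168 + 0.134 = 44%.

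**4. Nominal count if no covariate matters.** Expected false positives = covariates × levels × events × 0.05. Under SAP 8.1.1 the threshold cannot rise, so holding the level and dropping a level are complements. That leaves two distinct events.

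| Covariates | Levels | Events | Tests | Expected |
|---|---|---|---|---|
| 14 | 4 | 1 | 56 | 2.8 |
| 14 | 4 | 2 | 112 | 5.6 |
| 14 | 5 | 2 | 140 | 7.0 |
| 3 | 4 | 1 | 12 | 0.6 |
| 5 | 4 | 2 | 40 | 2.0 |

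Correlation between tests does not change these expectations.

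**5. Allowing for small strata.** The 4 v 5 Fisher test does not attain 5%. With a common loss probability of 0.5 its size is 20/512 = 3.9%; at 0.2 or 0.8 it is 1.2%. An interval-censored log-rank test was also simulated under no effect (weeks uniform on 1 to 17, exponential loss with median 6 or 12 weeks, covariate prevalence 50% or 25%).
- 11 per stratum: rejection 2.8 to 3.8% (asymptotic) or 1.4 to 2.1% (permutation); 4 to 11% of tests could not be computed.
- 9 per stratum: 2.7 to 3.4% or 0.8 to 1.5%; 10 to 20% not computable.

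At 2 to 3% per test, 56 tests give 1.1 to 1.7 false positives and 140 give 2.8 to 4.2. At the Fisher sizes, 140 give 1.7 to 5.5. Hence roughly 1 to 5.

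**6. After the change.** One test per covariate for one event: 14 × 0.05 = 0.7 expected. If the tests were independent, the chance of at least one is 1 − 0.95^14 = 51%, so a label or a rule is still needed. Holm's first step would be 0.05 / 14 = 0.0036. In the same simulation, a single unstratified test on 45 children rejected in 4.4 to 5.1% (asymptotic), close to nominal.

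**The case against.** The best defence is that this is a small estimation study. SAP 8.1 promises 95% confidence intervals with its tests, SAP 10.1 claims only an initial insight, and Objective #4 is worded cautiously. The SAP 9.3 list is for descriptive summaries, and at least four of its items (age, age at peanut introduction, skin test size, IgE) would need cut-points that the SAP does not give. Nothing shows that all 14 would be tested. Looking within month-48 level also has a reason, since the second primary objective is conditional on that level. All of this stands and limits the size of the problem. It does not supply the missing covariate list or multiplicity rule, and stratifying keeps the conditioning without splitting the sample.

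Stronger readings are tempting but unsupported:
- A reader might multiply 14 × 5 × 3 = 210 tests and infer 10.5 false positives. That counts two complementary events separately, takes the higher level count, assumes the 14 items are the groups, and ignores the low attained size in small strata.
- A reader might infer that significant predictors would be mostly noise. That share depends on true effects and power, which the documents do not give.
- A reader might give the SAP 8.1 P values primary-endpoint status. The hazard endpoint is answered by the coefficients of the SAP 10.1 model; a log-rank test does not estimate them.
- A reader might conclude that covariate effects must be secondary. SAP section 1 includes subject characteristics in its summary of the two main objectives, so the documents need reconciling but do not settle the direction.

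**Conclusion.** The point holds as a cheap improvement. Tests within each month-48 level, for unnamed groups and overlapping events at an unadjusted 0.05, have little power, and any significant result would rest on near-complete separation in a few children. The per-interval model in SAP 10.1 shares the weakness.

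The false-positive figures, 2.8 to 7 nominal and roughly 1 to 5 in practice, are conditional. They assume that the 14 listed characteristics are the groups, that no covariate matters, and that about 45 children spread evenly over four or five levels. With only 3 to 5 covariates the nominal figure is about 0.6 to 2. They count tests, not distinct covariates, since one covariate can be flagged at several levels or for both events. The conflict over role is plain in the text and depends on none of these assumptions.

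**What to change.** - **SAP 8.1:** name the covariates in advance, with cut-points for numeric ones where groups are needed. Replace the per-NOAEL tests with one interval-censored log-rank test per covariate, stratified by month-48 level, for one chosen loss event.
- **SAP 10.1:** fit one model across levels, with month-48 level as a stratum or a term, in place of a separate model per dose interval.
- **Reporting:** give covariate effects as estimates with 95% confidence intervals, labelled exploratory, with no significance claim. If claims are wanted, state a Holm rule over the named covariates.
- **Role:** give the covariate analyses one role, the same in the protocol synopsis, Protocol 2.1 and 2.2.1, and SAP 3.1.2 and 3.2.1.

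The cost is wording in both documents; no new data or change in conduct is needed. The pooled analysis assumes a common covariate effect across month-48 levels, and there will be fewer nominally significant results.

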8.1.1 Statistical Assumptions

Time to Loss of Desensitization (TLD) requires more rigorous mathematical framework of stochastic process. However, a good approximation could be achieved using Interval Censoring framework for the latter three events defined in section 3.2.1 (bullet 3). The framework uses following assumptions:

- Desensitization is monotonically decreasing with time. $NOAEL(\text{final DBPCFC}) \leq NOAEL(48\text{th month DBPCFC})$
- Subject's true sensitivity threshold at the 48th month DBPCFC is approximated by his/her NOAEL.
- Subjects with the final DBPCFC NOAEL higher than the 48th month DBPCFC NOAEL will be regarded as exceptions. Their final DBPCFC NOAEL will be considered equal to the 48th month DBPCFC NOAEL for conservative time to loss of desensitization estimates.
- Subjects with 48th month LOAEL < MCRT will also fail at LOAEL administered at the final DBPCFC that are less than MCRT, thereby un-necessitating the need for the final DBPCFC.
- Since the final DBPCFC observation times are randomized, subject's unobserved time to loss of desensitization and the baseline covariates are independent of his/her final DBPCFC observation time.

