## **8. STATISTICAL CONSIDERATIONS**

For full description of statistical considerations, please refer to the statistical analysis plan. A summary of the plan is described below. Unless otherwise indicated, all statistical tests will be 2 sided and tested at a significance level of 0.05. Corresponding 95% confidence intervals will be presented for statistical tests.

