### **8.1 Study Endpoint Assessment**

#### **8.1.1 Primary Endpoint**

The primary endpoint is defined in Section 2.2.1. First, an Interval-Censoring Survival Analysis (ICSA) approach will be used to analyze the 48th month DBPCFC threshold data (Collett, 1993, Chapter 9, Taylor et al - 2009). Parametric (Log-normal, Weibull) and non-parametric dose-distribution model will be used to estimate the ED10 and the ED05, the doses predicted to provoke reactions in 10% and 5%, respectively, of the peanut-allergic population. Second, for each dose interval bounded by the NOAEL and LOAEL of the 48th month DBPCFC, we will conduct survival analysis with case-1 censoring (Huang – Wellner lecture notes, Kosorok et al, 1998) to estimate time to loss of desensitization.

Sample size was originally calculated for 80% power of detecting a p-value of 0.05 considering 2:1 placebo:peanut SLIT randomization and estimating a 50% pass rate for those randomized to placebo versus a 90% pass rate for those randomized to continue peanut SLIT . Adjusting for an estimated 10% drop out rate resulted in a minimum required sample size of 50 subjects. The sample size for the amended study has not been revised from the estimated minimum required size of 50 subjects since the study is in progress with an existing enrollment of 51 subjects. We intuitively think this number is adequate with the amended study design and analytical methods for the revised primary outcome of interest. However, to confirm our understanding, we plan on conducting simulations to study the power-sample size curve at 80% power based on study assumptions as discussed in the statistical methods section of the statistical analysis plan.

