1. BACKGROUND

This Statistical Analysis Plan (SAP) has been written to address the concerns identified in the March 19, 2014 protocol abbreviated Peanut SLIT and Tolerance (UNC IRB#11-2308), which included our proposed primary analysis plan aimed at assessing effectiveness of peanut SLIT to induce clinical tolerance 6 months after its discontinuation.

We recognize the investigating team's concerns regarding the assumption that patients will be able to clear the food challenge administered after 6 months of SLIT discontinuation to demonstrate clinical tolerance. The team believes this assumption is rather optimistic, less supported by prior research and suspects that the current study protocol calls for negligible success rate by the end of 6 months of SLIT discontinuation as most of the subjects would fail for clinical tolerance. Since time to loss of desensitization (TLD) is an important dimension that, in our knowledge, no prior study has investigated, provides clinically valuable information and helps facilitate future study design, this study provides an opportunity and a robust framework to study the same. As a result, the revised protocol analyzes a systematic approach to address this concern. We believe that with few changes in the study design and efficacy analysis plan, the revised protocol will help address new objectives of primary enquiry and will provide greater precision to cater to individual's need.

With 51 total enrollees, we are midway through the study's conduct with 24 subjects clearing 48 months of dose maintenance period and waiting to be administered the 48th month food challenge and to be randomized to the placebo or the treatment arm as per the existing protocol. The revised study design calls for amendments beyond the 48 months' period of dose maintenance to include 48th month food challenge followed by discontinuation of SLIT for all subjects for at most 17 weeks, dissolving the need for a two-arm trial. Subjects will be randomized to weekly observed time points during 17 weeks following the 48th month food challenge when the final food challenge will be administered to assess individual's persistent desensitization also known as sustained unresponsiveness (SU). The structure of this final food challenge will be similar to that of the earlier (48th month) food challenge with similar levels of administered drug doses.

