4.3 Method of Week Assignment for the Final Challenge and Randomization

The following criteria must be satisfied in order for the patient to continue to the SU phase of the study and be randomized:

1. The patient achieves MCRT at the 48th month DBPCFC to continue to the SU phase. This requires patient to be asymptomatic upon administration of 300 mg dose as assessed by Food Challenge Symptom Score sheet.
2. If subjects are found symptomatic and AEs that occur are considered to be intolerable at or below the MCRT, subjects will be refrained from taking the final challenge and will be considered to have lost their desensitization at week 0.
3. No subject will be administered a final challenge dose higher than the NOAEL attained at the 48th month DBPCFC.

Before the start of the SU phase of the study, a computer-generated block randomization schedule is prepared such that each subject has an equal probability of being randomized to one of the weekly challenges held in initial 6 weeks, between 7-12 weeks and between 13-17 weeks. Based on the randomization schedule, three qualified subjects are randomly assigned to one of the final DBPCFC administered each week during the study's 17-week SU phase.

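### Chance drops between two single food challenges are counted as loss over time off SLIT, so time to loss for the one-level events is biased short

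*SAP*

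**What the plan says.** - **No zero-avoidance reference.** Under the earlier design some children would have continued SLIT. SAP section 1 now has the month-48 challenge "followed by discontinuation of SLIT for all subjects for at most 17 weeks, dissolving the need for a two-arm trial". Protocol 5.9 assigns avoidance intervals of 1 to 17 weeks, so no child is re-challenged while still on SLIT.
- **Selection.** SAP 4.3 requires: "The patient achieves MCRT at the 48th month DBPCFC to continue to the SU phase".
- **Event.** SAP 3.2.3 defines loss as a decline from the month-48 to the final challenge. The primary events in SAP 3.2.1 include "Subject's true sensitivity threshold to drop by at least one level of LOAEL", staying at the same level, and remaining at or above the MCRT of 300 mg.
- **Measurement.** SAP 8.1.1 assumes that desensitization can only fall with time and approximates the true month-48 threshold by the NOAEL. Rises are treated as exceptions: "Their final DBPCFC NOAEL will be considered equal to the 48th month DBPCFC NOAEL for conservative time to loss of desensitization estimates".
- **Model.** SAP 10.1 fits a current-status likelihood with F(t) = 1 − exp(−λt) within each month-48 dose interval. The separate probability of loss at time zero is for children below the MCRT at month 48. SAP 10.1 also plans a semi/non-parametric check of the exponential form.

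Neither document gives a figure for challenge repeatability or an allowance for it.

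**The concern.** Two challenges in the same child can stop at different dose steps although nothing has changed biologically. Under this plan a chance fall is an event and a chance rise is a non-event. Because F(0) = 0 among challenged children, the model can explain a chance fall only as decay during avoidance. Time to loss for the one-level-drop and same-level events then comes out too short, and the proportions lost at fixed times too high.

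These are primary endpoints. Protocol 2.1 wants the decay curve to inform the dosing interval and the effect of missed doses. For that use, an overstated rate of loss is an error, not caution. The SAP's word conservative fits only a claim that protection lasts.

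**Working it through.** **1. The plan's own sample size.** Protocol 8.1.1 states "Sample size was originally calculated for 80% power of detecting a p-value of 0.05 considering 2:1 placebo:peanut SLIT randomization", with "50% pass rate for those randomized to placebo versus a 90% pass rate for those randomized to continue peanut SLIT"; tests are two-sided at 0.05 (Protocol section 8).
- Pooled rate: (0.9 + 2×0.5)/3 = 0.633.
- n(SLIT) = [1.960×√(1.5×0.633×0.367) + 0.842×√(0.09 + 0.25/2)]² / 0.4² = (1.157 + 0.390)²/0.16 = 14.96, so 15.
- With 30 on placebo the total is 45, and 45/0.9 = 50. This matches "Adjusting for an estimated 10% drop out rate resulted in a minimum required sample size of 50 subjects".

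The 50 is reproduced, but it belongs to a comparison that included children continuing SLIT. That reference is gone.

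**2. How often a level is lost by chance.**
- Individual doses of 100, 200, 500, 800, 1300 and 2100 mg (SAP 4.2) give cumulative steps of 100, 300, 800, 1600, 2900 and 5000 mg.
- Assumed, not in the documents: log-normal thresholds with median 1000 to 3000 mg and between-child ln SD 1.0 to 1.3; variation at each challenge with ln SD 0.2 to 0.7; no true change.
- Children with a month-48 NOAEL of at least 300 mg are kept.

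Simulated results:
- Drop of at least one level: about 13 to 39%. If 0.2 to 0.7 is instead the SD of the difference between two challenges: about 9 to 33%.
- Rise of at least one level: about 12 to 31%.
- Fall below 300 mg: about 0.3 to 10%.
- Share of the drop rate due to month-48 selection: about 0 to 6 percentage points.

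A second simulation (between-child log10 SD 0.5, per-challenge log10 SD 0.1 to 0.4, medians 800 to 2900 mg) gave 15 to 44% false drops and 1 to 15% false falls below 300 mg.

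**3. What the exponential model makes of it.** With equal numbers at weeks 1 to 17 and expected event probability q(t), λ maximizes Σ[q(t)·ln(1 − e^(−λt)) − (1 − q(t))·λt]. The fitted median is ln 2/λ.

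No true loss, q(t) = p0 in every week:

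| p0 | λ per week | fitted median (weeks) | fitted loss at week 17, 1 − e^(−17λ) |
|---|---|---|---|
| 20% | 0.0248 | 28 | 34% |
| 30% | 0.0397 | 17 | 49% |
| 40% | 0.0571 | 12 | 62% |

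True median 16 weeks, q(t) = p0 + (1 − p0)(1 − 2^(−t/16)):
- p0 = 20%: fitted median 9.9 weeks. Loss at week 17 is fitted as 1 − 2^(−17/9.9) = 70%, against a true 1 − 2^(−17/16) = 52%.
- p0 = 30%: fitted median 8.1 weeks.

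**4. Whether the data could estimate p0.** Protocol 5.2 expects about 45 children, or 45/17 = 2.6 per week; SAP 4.3 assigns three. No losses in three children at week 1 still leaves a 95% upper limit of 1 − 0.025^(1/3) = 71%. With 45 children, true p0 of 20% and a true 16-week median, the estimated p0 ranges from 0 to about 40% or more (5th to 95th percentile).

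**The case against.** Four points on the other side deserve weight.

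- **The reset rule.** A reader might infer that resetting rises creates losses. It does not. The analysed outcome is a yes/no indicator, and a rise is no loss with or without the reset. Deleting the rule would change no indicator and no fitted λ. The drivers are the any-decline event, the NOAEL taken as truth, and F(0) = 0.
- **Selection.** A reader might infer that regression to the mean after the month-48 criterion explains most of the effect. In the simulations it adds only about 0 to 6 points.
- **The planned check.** A reader might infer that the semi/non-parametric check is worthless. It is not. Weeks are randomized, so pure noise appears as a loss rate that is flat in time, which is a departure from the exponential form. A one-sided 5% test for an intercept with 45 children has power of roughly 60 to 70% against flat 20% noise, 75% against 30% and 85% against 40%. With 20 to 30% noise on top of a true 16-week median, power is only about 30 to 50%. The SAP does not specify the form of the check, and analysis by dose interval weakens it. It is a partial safeguard.
- **Size.** Every magnitude above rests on assumed repeatability. That stands: only the direction follows from the documents.

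**Conclusion.** The point holds as a directional bias. For the one-level-drop and same-level events, challenge-to-challenge variation is counted as loss over time, so time to loss is too short and the proportions lost at fixed times are too high. With no true change, about 13 to 39% of eligible children would drop a level if the ln SD of 0.2 to 0.7 applies to each challenge, or about 9 to 33% if it applies to the difference. The MCRT event is much less affected, at about 0.3 to 10% on the same assumptions. The documents do not support a single figure for the bias, nor a statement that the plan has no protection against it.

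**What to change.** - Add to SAP 10.1 a sensitivity analysis with F(t) = p0 + (1 − p0)(1 − exp(−λt)) at fixed p0 of 0, 10, 20 and 30%, pooled over month-48 dose intervals. Do not rely on an estimated p0 at this sample size.
- State that one-level drops include challenge variation. Report the at-or-above-MCRT event, already listed in SAP 3.2.1, alongside as the less affected result.
- Tabulate any observed rises beside drops, without overwriting them.
- Reconcile three passages. SAP 4.3 item 3 bars a final dose above the month-48 NOAEL, Protocol 5.6 makes the final challenge identical to that at month 48, and SAP 8.1.1 provides for higher final NOAELs. Use the observed rise rate as a further p0 value only if rises prove observable. The fixed-p0 analysis works either way.

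The cost is SAP wording, one extra table and a wider range of reported times to loss. No visits or children are added.
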